5 SAFETY ANALYSIS STRATEGY

5.1 Safety Endpoints

Safety endpoints are:

- All adverse events (ocular and nonocular, serious and non-serious)
- Secondary surgical interventions (SSIs)
- Device deficiencies
- IOL observations

- IOL position change (tilt and decentration)
- Posterior Capsule Opacification (PCO)
- Posterior capsulotomy
- Surgical problems
- Other surgical procedures at surgery
- Slit lamp examination
- Dilated fundus examination
- Intraocular Pressure (IOP) (mmHg)

5.2 Safety Hypotheses

There are no formal safety hypotheses in this study. The focus of the safety analysis will be a comprehensive descriptive assessment of safety endpoints listed in Section 5.1.

5.3 Statistical Methods for Safety Analyses

Except otherwise stated, the analysis set for all safety analyses is the SAS as defined in Section 2.2. Baseline will be defined as the last measurement prior to exposure to investigational product, except otherwise stated.

Unless otherwise specified, all eye-level safety endpoints will be summarized by treatment, separately for first implanted eyes and second implanted eyes, as well as for all eyes combined. When combining eyes, mixed effects models will be utilized to account for the correlation between subject-eyes when estimating confidence intervals.

In addition to the analyses presented below a listing of all monocular BCDVA for eyes with a loss of 10 letters or more at 3 months compared to 1 month will be provided; where a 10 letter loss (decrease) is a change in BCDVA of at least 0.2 logMAR.

5.3.1 Adverse Events

The applicable definition of an Adverse Event (AE) is in the study protocol. The number and percentage of all ocular adverse events will be tabulated for any event and by MedDRA Preferred Term by treatment. An eye with multiple ocular AEs of the same preferred term is only counted once toward the total of this preferred term. The number of events will also be presented. Adverse events related to the study IOL are referred to as adverse device effects.

Additionally, adverse events associated with SSI, specifically with preferred terms indicating secondary IOL intervention, will be summarized by relatedness to the study device by treatment. For SSIs, the number of events is not applicable and therefore will not be presented.

Adverse events will be summarized in the following tables, by treatment:

1. All Adverse Events (Serious and Non-Serious Combined)
 - a. Ocular
 - b. Nonocular
2. All Adverse Device Effects
 - a. Ocular
 - b. Nonocular
3. All Serious Adverse Events (including Serious Adverse Device Effects)
 - a. Ocular
 - b. Nonocular
4. Secondary Surgical Interventions (SSIs)
3. Subject/Eye Listings
 - a. Non-serious Ocular
 - b. Non-serious Nonocular
 - c. Serious Ocular
 - d. Serious Nonocular
 - e. SSIs

In addition, listings of treatment-emergent and non-treatment emergent adverse events will be provided separately. The treatment-emergent AE listings will include, but are not limited to, the following variables: IOL model, subject identification number, age, sex, surgery eye (first or second implanted eye), eye (OD or OS), days from surgery, AE duration, and corresponding AE details.

Individual subject listings will be provided for AEs that occur after signing informed consent but prior to exposure to investigational product (i.e., non-treatment emergent). The non-treatment emergent AE listings will include, but are not limited to, the following variables: subject identification number, age, sex, eye (if applicable), days prior to planned surgery, duration, and corresponding AE details.

A listing of all SSIs will also be presented and will include, but is not limited to, the following variables: IOL model, subject identification number, age, sex, eye, days from surgery, duration, and corresponding AE details

Ocular AEs and SSIs will also be summarized by toric and non-toric lenses for all eyes combined only.

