	
immediate risk of death from the event as it occurred, i.e., it does not include an event which hypothetically might have caused death had it occurred in a more severe form.
 
b) any potentially sight-threatening event or permanent impairment to a body structure or a body function.
 
c) inpatient hospitalization or prolonged hospitalization. Note: Planned hospitalization for a preexisting condition, without serious deterioration in health, is not considered a serious adverse event. In general, hospitalization signifies that the individual remained at the hospital or emergency ward for observation and/or treatment (usually involving an overnight stay) that would not have been appropriate in the physician's office or an outpatient setting. Complications that occur during hospitalization are adverse events. If a complication prolongs hospitalization or fulfills any other serious criteria, the event is serious. When in doubt as to whether "hospitalization" occurred, the event should be considered serious.
 
d) a medical or surgical intervention to prevent a) or b). This includes any ocular secondary surgical intervention excluding posterior capsulotomy.
 
e) any indirect harm as a consequence of incorrect diagnostic test results when used within manufacturer's instructions for use.
 
 • Fetal distress, fetal death, a congenital abnormality or birth defect. 
Refer to Section 11 for additional SAEs.

Serious Health Threat
	
Any event type which results in imminent risk of death or a serious deterioration in state of health, or serious illness that requires prompt remedial action.
 
This would include: Events that are of significant and unexpected nature such that they become alarming as a potential public health

	hazard, e.g., human immunodeficiency virus (HIV) or Creutzfeldt-Jacob Disease (CJD).
Study Start	The start of the study is considered to coincide with the enrollment of the first subject.
Study Completion	The completion of the study is considered to coincide with the study-level last subject last visit or the decision to terminate the trial, whichever is later.
Unanticipated Serious Adverse Device Effect (USADE)	Serious adverse device effect which by its nature, incidence, severity, or outcome has not been identified in the risk assessment.

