5.3 Risks and Benefits

The clinical investigation process risks are managed through appropriate training and monitoring according to the protocol-specific monitoring plan. Investigational device risks, including risks associated with use of device and methods and procedures for application of device, are defined in the product labeling and are managed through review of safety assessments outlined in this protocol.

Complications may occur on the surgery day or throughout the postoperative period. As with any type of intraocular surgery, there is a possibility of complications due to anesthesia, drug reactions, and surgical problems. The surgical procedure can exacerbate a pre-existing ocular condition. Possible problems during surgery include: corneal endothelial touch, detached Descemet's membrane, iris damage, iris prolapse, iris trauma, iris incarceration, zonular rupture, vitreous loss, capsulorhexis tear, capsular rupture, uncontrollable IOP, hyphema and retinal damage. An IOP increase may occur from the surgical procedure, residual viscoelastic in the eye or a steroid response to postoperative medications.

Additionally, potential postoperative adverse events include but are not limited to: corneal stromal edema, cystoid macular edema, endophthalmitis, hypopyon, iritis, lens dislocation, membrane formation on the IOL, pupillary block, retinal detachment, cyclitic membrane, transient or persistent glaucoma, retinal tear, vitritis, iris touch, pupil ovalization, posterior synechiae, ocular inflammation, ocular discomfort or pain, inflammation, decreased vision, decreased contrast sensitivity, decreased color perception, visual disturbances and corneal endothelial cell loss.

An IOL replacement or explantation may be appropriate in some cases of significant residual refractive error, ocular infection, subject dissatisfaction. In most of cases, spectacles or contact lenses may be prescribed to resolve residual refractive error. Other secondary surgical interventions include but are not limited to: IOL repositioning, refractive laser treatment, paracentesis, vitreous aspirations, iridectomy or laser iridotomy for pupillary block, wound leak repair, and retinal detachment repair.

There may also be unknown risks with the use of the Clareon/Clareon Toric or Eyhance/Toric IOLs. Any foreseen risk to subjects in this clinical study will be minimized by compliance with the eligibility criteria, study procedures, and clinical monitoring.

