10.3 Unscheduled Visits

An unscheduled visit (USV) is defined as follows:

- Ocular examination that is not standard of care and not required by the protocol
- Examination conducted by the study staff
- New findings, or a change to a previous finding was discovered

- Not site standard of care (SOC)/routine

An USV may or may not result in the capture of an adverse event. Likewise, an adverse event may be captured without the report of an USV (e.g., AE identified subsequent to study eye examination by non-study personnel).

If a subject visit occurs between any regularly scheduled visit and the visit is conducted by study personnel, this visit must be documented as an USV. If the subject seeks medical attention outside the clinic (for example, at an Emergency Room) or at the clinic but is seen by non-study personnel, the investigator is to capture adverse event-related information on the Adverse Event form upon becoming aware.

The assessments captured at the USV are dictated by the Investigator per his/her medical judgement, however, the following assessments are recommended

- Collect Adverse Event information.
- Record changes in medical condition or concomitant medication

- Measure monocular BCDVA at 4 m [REDACTED].
- Perform tonometry.

- Perform a slit-lamp examination.

- Record IOL observations, if any, for the operative eye(s).

- Perform a dilated fundus examination.
- Record any subjective posterior capsule opacification if present and information for any posterior capsulotomy that has occurred since surgery, if applicable for operative eye(s).
- Record secondary surgical interventions for the operative eye(s) that have occurred since surgery, if applicable.

- Record any adverse events (both volunteered and elicited).
- Record any device deficiencies, if applicable.

Note: Assessments that may be completed during an unscheduled visit are not limited to the above list. In cases where the Investigator's routine clinic visits are more frequent than study specific visits the additional routine visits would not be considered as unscheduled visits.

However, adverse events collected from these routine visits must be reported with the study data. Refer to Section 11 for further details on the AE reporting.

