11 ADVERSE EVENTS AND DEVICE DEFICIENCIES

11.1 General Information

An AE is any untoward medical occurrence, unintended disease or injury, or untoward clinical signs (including abnormal laboratory findings) in subjects, users, or other persons, whether or not related to the investigational medical device (test product). Refer to the Glossary of Terms for categories of AEs and SAEs.

Figure 11-1 **Categorization of All Adverse Events**

[figure not shown]
[figure not shown]

Figure 11-2 **Categorization of All Serious Adverse Events**

Specific Events Relevant to this Protocol

In addition to reporting all AEs (serious and non-serious) meeting the definitions, the Investigator must report any occurrence of the following as an SAE:

Cumulative (at any visit during the study) Serious Adverse Events:

- Cystoid macular edema
- Hypopyon
- Endophthalmitis
- Lens dislocation
- Pupillary block
- Retinal detachment
- Secondary surgical intervention (excluding posterior capsulotomy)

Persistent (still present at conclusion of study) Serious Adverse Events:

- Corneal stromal edema
- Cystoid macular edema
- Iritis
- Elevated IOP requiring treatment

Any other potentially sight-threatening event may also be considered serious based on the judgment of the Investigator and should be reported appropriately as delineated in Section [11.3](#).

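### Does SAP 5.3.1 confine the secondary surgical intervention table to procedures on the lens, leaving out other secondary eye surgery that the protocol counts?

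*SAP*

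**What the plan says.** SAP 5.1 lists "Secondary surgical interventions (SSIs") among the safety endpoints with no qualifier, as do the endpoint lists in Protocol 3, 6.5 and 12.6. SAP 5.2 promises a "comprehensive descriptive assessment of safety endpoints listed in Section 5.1".

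The protocol shows the breadth of the term in three places:

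- The glossary entry for serious adverse events, at item d, states: "This includes any ocular secondary surgical intervention excluding posterior capsulotomy".
- The mandatory serious event list in Protocol 11.1 contains "Secondary surgical intervention (excluding posterior capsulotomy").
- Protocol 5.3 says that "An IOL replacement or explantation may be appropriate in some cases of significant residual refractive error". It then names lens repositioning together with "refractive laser treatment, paracentesis, vitreous aspirations, iridectomy or laser iridotomy for pupillary block, wound leak repair, and retinal detachment repair".

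SAP 5.3.1 deals with SSIs in several outputs. An additional summary by relatedness to the device covers "adverse events associated with SSI, specifically with preferred terms indicating secondary IOL intervention". The list of tables has a separate SSI entry (item 4) with no selection rule. There are also a listing of all SSIs and a summary of SSIs by toric and non-toric lenses, neither of them restricted.

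**The concern.** The preferred-term phrase is the only selection rule for SSIs anywhere in SAP 5.3.1, and only one SSI table is listed after it. The SAP refers to the protocol for the definitions of adverse event and device deficiency but gives no such pointer for SSI. A programmer could therefore take item 4 to be the lens-only summary.

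The table titled SSI would then show a narrower set than the protocol's wording covers. The adverse event tables would not supply the missing total directly. They are specified for any event and by preferred term, so their overall row mixes SSIs with other events, and preferred-term rows cannot be added because one eye may appear in several. At stake is the by-arm number and percentage of eyes with any SSI, for an event that the protocol always treats as serious.

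**Working it through.** The plan states no figure for SSIs, so there is none to reproduce. The check is a comparison of texts, followed by a rough scale.

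**1. Which output does the restriction govern?** The sentence in SAP 5.3.1 opens by marking itself as an addition to the main tabulation, and its verb concerns relatedness to the device. Item 4 is a separate entry under the endpoint's own name. The restricting phrase itself narrows a wider SSI category; if SSI already meant lens procedures only, it would do no work. The same section also promises a listing of all SSIs, so it uses the term without limit elsewhere.

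**2. What applies where nothing is specified?** Three passages combine:

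| Source | Content |
|---|---|
| SAP 5.1 | SSI is an endpoint, unrestricted |
| SAP 5.3, opening text | Unless specified otherwise, each eye-level safety endpoint is summarized by treatment, for first eyes, second eyes and all eyes |
| Protocol 12.6 | SSI is an endpoint, unrestricted; categorical safety measures get sample size, number and percentage |

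Nothing in SAP 5.3.1 specifies otherwise for item 4. The natural reading is a by-arm number and percentage of eyes for all SSIs. The remark in SAP 5.3.1 that event counts do not apply to SSIs fits a table that counts eyes.

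**3. What would be lost on the narrow reading?** Protocol 5.3 names these procedures, with iridectomy and laser iridotomy counted as one:

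- On the lens: replacement, explantation, repositioning = 3.
- Not on the lens: refractive laser, paracentesis, vitreous aspiration, iridectomy or iridotomy, wound leak repair, retinal detachment repair = 6.

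So 6 of 9 named types would fall outside a lens-only table. This counts names in a risk paragraph and says nothing about frequency.

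Those six types would not disappear from the report. The glossary and Protocol 11.1 make every SSI other than posterior capsulotomy a reportable serious event, so each reaches the ocular adverse event and serious adverse event tables by treatment, and the listing of all SSIs. Posterior capsulotomy has its own table under SAP 5.3.5.

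**4. Are the data there?** The schedule in Protocol Table 3-1 collects adverse events including SSIs at every visit. For unscheduled visits, Protocol 10.3 recommends: "Record secondary surgical interventions for the operative eye(s) that have occurred since surgery, if applicable". Neither is limited to lens procedures.

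**5. Scale.** With 84 planned randomized subjects per arm and both eyes treated, 84 × 2 = 168 eyes, and one eye is 1/168 = 0.60%. With 70 planned completers, 70 × 2 = 140 eyes and 1/140 = 0.71%. The safety set takes all eyes with attempted implantation (SAP 2.2), so the first figure is the closer one. Both give the weight of one eye, not the size of an error.

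**The case for a change.** The strongest case for a change is that two competent programmers could fill a table of the same title with different events. The paragraph containing the restriction is the only text on how an SSI summary is built, its next sentence speaks of SSIs in general, and a single SSI entry follows in the table list. The preferred terms are not enumerated. Protocol 5.2 foresees publication, and the scope of a serious-event table is better settled before by-arm data are visible. A sentence would cost almost nothing.

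Part of this stands. The SAP does not say in so many words which events fill item 4 or the toric/non-toric summary, and a clarifying sentence would do no harm. But the lens-only reading has to set aside the default rule in SAP 5.3 and the unrestricted endpoint lists.

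The claim that the protocol defines the endpoint as all ocular secondary surgery except capsulotomy also goes a little too far. The endpoint lists say only SSI; the fuller wording comes from the seriousness criterion and the serious event list, and Protocol 5.3 is a description of risks.

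Nor is there a case for widening the by-relatedness summary. Confining a device-relatedness summary to procedures on the device is a legitimate choice and contradicts nothing in the protocol.

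**Conclusion.** No change to the plan is called for. The restriction applies to one additional summary. Read with SAP 5.1, the default rule in SAP 5.3 and Protocol 12.6, the SSI table and the toric/non-toric summary cover all SSIs. What remains is a small gap in detail that an analyst following those sections would fill correctly when drafting the table shells.

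If the gap were filled the other way, the consequence would be one descriptive subtotal missing from the tables and recoverable from the listing. Its size cannot be given because the documents state no SSI rate. SAP 5.2 sets no safety hypothesis, and the primary noninferiority comparison does not use these data.

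This conclusion assumes that SSIs are reported as serious events as the protocol requires, and that the listing of all SSIs is produced as the SAP states.

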5.3.2 Device Deficiencies

The applicable definition of a device deficiency is presented in the study protocol. The number and percentage of all device deficiencies will be tabulated by treatment. A listing of all device deficiencies will also be provided. Device deficiencies will be summarized and listed for all randomized subjects.

Device deficiencies will also be summarized by toric and non-toric lenses for all eyes combined only.

5.3.3 IOL Observations

The number and percentage of IOL observations reported at each scheduled visit will be tabulated by treatment. A listing of all IOL observations will also be provided.

IOL observations will also be summarized by toric and non-toric lenses for all eyes combined only.

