5.3.4 Subjective Posterior Capsule Opacification (PCO) Assessment

The number and percentage of eyes representing the maximum rating for an eye during the study will be tabulated by the response categories presented on the CRF (i.e., none, clinically nonsignificant, clinically significant, clinically significant requiring a YAG) and summarized by treatment. Similarly, eyes with a ‘worst case’ rating of clinically significant PCO or posterior capsulotomy (YAG) will be summarized by the response categories on the CRF. The summaries described above will also be further summarized by toric and non-toric lenses, for all eyes combined only.

A listing of eyes with clinically significant PCO, clinically significant PCO requiring YAG, or posterior capsulotomy will be presented which includes the PCO or capsulotomy results at all visits. The listing will include, but are not limited to, the following variables: treatment, IOL model, subject identification number, age, sex, surgery eye (first or second implanted eye), eye (OD or OS), visit, days from surgery, and PCO or capsulotomy details at each visit.

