5.3.8 Slit Lamp Examination

For each slit lamp parameter as per the CRF, numbers and percentages of eyes that experience an abnormality at each scheduled visit will be presented by treatment.

A listing will be provided which presents all eyes with an abnormality in any slit-lamp parameter at any postoperative visit. The listing will include all slit-lamp data from all visits with the following variables: treatment, subject identification number, age, sex, surgery eye (first or second implanted eye), eye (OD or OS), visit, days from surgery, and slit lamp parameter.

Slit lamp abnormalities will also be summarized by toric and non-toric lenses for all eyes combined only.

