5.3.9 Dilated Fundus Examination

For each dilated fundus parameter as per the CRF, numbers and percentages of eyes that experience abnormality at each scheduled visit will be presented by treatment.

A listing will be provided which presents all eyes with an abnormality in any fundus parameter at any postoperative visit. The listing will include all fundus examination data from all visits with the following variables: treatment, subject identification number, age, sex, surgery eye (first or second implanted eye), eye (OD or OS), visit, days from surgery, and fundus parameter.

Dilated fundus abnormalities will also be summarized by toric and non-toric lenses for all eyes combined only.

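### The by-arm IOL-observation, slit-lamp and fundus tables count scheduled visits only, so a transient finding made at an unscheduled visit and not reported as an adverse event appears only in a listing

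*SAP*

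**What the plan says.** Three safety endpoints are tabulated by treatment for scheduled visits only:

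- IOL observations (SAP 5.3.3): "The number and percentage of IOL observations reported at each scheduled visit will be tabulated by treatment".
- Slit lamp (SAP 5.3.8): "numbers and percentages of eyes that experience an abnormality at each scheduled visit will be presented by treatment".
- Dilated fundus (SAP 5.3.9): "numbers and percentages of eyes that experience abnormality at each scheduled visit will be presented by treatment".

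The listings are wider. For IOL observations, "A listing of all IOL observations will also be provided". For slit lamp, "A listing will be provided which presents all eyes with an abnormality in any slit-lamp parameter at any postoperative visit", and the fundus listing has the same scope. The slit-lamp and fundus listings carry treatment as a variable; the IOL-observation listing names no variables.

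Protocol 10.3 includes this among the elements that define an unscheduled visit: "New findings, or a change to a previous finding was discovered". It recommends a slit-lamp examination, a dilated fundus examination and recording of IOL observations there. The visit schedule (Protocol Table 3-1, SAP Table 10-1) provides for all three at that visit as necessary.

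For PCO, SAP 5.3.4 tabulates by treatment "The number and percentage of eyes representing the maximum rating for an eye during the study".

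**The concern.** The by-visit tables give the proportion of eyes with a finding on a few fixed examination days. They do not give the proportion of eyes ever affected. Unscheduled visits are where new or changed findings between those days tend to be recorded, and the by-arm counts leave them out by rule. The SAP gives no reason for treating these three endpoints differently from PCO, or for giving each table a narrower scope than its own listing. SAP 5.2 commits to a comprehensive description of the safety endpoints. For short-lived findings, these tables fall short of that.

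**Working it through.** The documents state no figure on this point, so the check compares scopes and then works out the timing and the unit of size.

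**1. Visit scope of the by-treatment safety summaries in the SAP**

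| Endpoint | By-treatment table | Listing |
|---|---|---|
| IOL observations (5.3.3) | scheduled visits | all observations |
| Slit lamp (5.3.8) | scheduled visits | any postoperative visit |
| Dilated fundus (5.3.9) | scheduled visits | any postoperative visit |
| PCO (5.3.4) | maximum during the study | eyes with clinically significant PCO or capsulotomy, all visits |
| Posterior capsulotomy (5.3.5) | no visit limit stated | in the PCO listing |
| Ocular AEs, ADEs, SAEs, SSIs (5.3.1) | no visit limit stated | yes |

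All three named tables have the limit, and none has an any-visit or worst-case row. Each section also plans a toric/non-toric summary; in 5.3.3, "IOL observations will also be summarized by toric and non-toric lenses for all eyes combined only". These summaries state no visit scope. I read them as following the table above them, but a programmer could read them otherwise.

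**2. Which findings drop out of every by-arm count**

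Four conditions must all hold:

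1. The finding is made at an unscheduled visit.
2. It is not seen at any scheduled examination, so it has resolved before the next one.
3. It is not reported as an AE.
4. It is not captured by another endpoint tabulated without a visit limit, such as PCO or capsulotomy.

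Condition 3 can occur. Protocol 10.3 states that an unscheduled visit need not produce an AE. Protocol 11.3 requires AE reporting only when the investigator judges the change clinically relevant. Protocol 11.4 exempts typical early postoperative findings, such as cells and flare or corneal edema, if they can be expected to clear within a week without lasting visual effect.

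**3. How long a finding can go between scheduled examinations**

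Inputs: the visit windows in Protocol 7.1 and Table 3-1. Visits 2A and 3A are timed from second-eye surgery.

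- Slit lamp and IOL observations, second eye, Visit 1A (Day 1-2) to Visit 2A (Day 30-60): shortest 30 − 2 = 28 days, longest 60 − 1 = 59 days.
- Visit 2A to Visit 3A (Day 90-120), all three assessments: shortest 90 − 60 = 30 days, longest 120 − 30 = 90 days.
- First eye: the first gap is up to 14 days longer if the recommended interval between surgeries is kept, so up to 59 + 14 = 73 days.
- Fundus: no examination is scheduled at Visit 1 or 1A. Each eye has two scheduled postoperative fundus examinations, against three for slit lamp and IOL observations. The first falls 30-60 days after second-eye surgery.

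**4. Unit of size**

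These tables use the safety analysis set (SAP 5.3), which is every eye with attempted implantation (SAP 2.2). About 84 subjects per arm are to be randomized for bilateral implantation: 84 × 2 = 168 eyes, or slightly fewer if some never reach surgery. One eye is 1/168 = 0.6%. The planned 70 completers per arm (140 eyes) are not the right base for a row that counts eyes ever affected.

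The documents give no rate of unscheduled visits, or of findings that meet all four conditions, so the number of eyes left out cannot be calculated.

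**The case against.** A reader might infer that findings from unscheduled visits enter no comparison between the lenses. The documents do not support that. Protocol 11.3 requires any clinically relevant untoward change in a study parameter to be reported as an AE, regardless of causality. SAP 5.3.1 tabulates ocular AEs by treatment with no visit limit, and Protocol 12.6 accounts for AEs from consent to study exit. A finding that persists is also counted at the next scheduled visit. The AE route is the plan's channel for important findings between visits, and it works for those.

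A reader might also infer that every unscheduled visit reflects a new finding. Protocol 10.3 lists that element, but it also requires any visit to study personnel between scheduled visits to be documented as unscheduled.

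The best defence of the present tables is comparability. Scheduled examinations are made at the same times in both arms. What is examined at an unscheduled visit is left to the investigator's judgement, and masking covers only the subject and the VA assessor (Protocol 9.4). A count that includes those visits may differ between arms because of ascertainment alone. This stands: it is a good reason to keep the scheduled-visit rows as the main comparison. It is not a reason to leave an any-visit count out.

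It is also true that the listings keep the data, so a reader with the slit-lamp and fundus listings could count by arm. A pre-specified row is still better than a hand count made after the results are known.

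**Conclusion.** The point holds in a narrow form. The three by-arm tables omit unscheduled visits, and a finding that meets all four conditions above appears only in a listing. This assumes that the toric/non-toric summaries take the same visit scope as the main tables.

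The effect is minor. The study has no safety objective or safety hypothesis (Protocol 6.5, SAP 5.2), and the primary analysis of binocular BCDVA is not touched. Each eye left out is about 0.6 percentage points of an arm. How many eyes that would be is unknown, and any total would only restate an assumed rate. The case for acting is that the remedy is cheap, uses data already collected, and matches what the SAP already does for PCO.

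**What to change.** In SAP 5.3.3, 5.3.8 and 5.3.9:

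- Keep the scheduled-visit rows unchanged as the main by-arm presentation.
- Add one supplementary row, 'any postoperative visit, scheduled or unscheduled', counting each eye once by treatment, with safety-analysis-set eyes as the denominator.
- In 5.3.3, count eyes rather than observations.
- Show the number of eyes with at least one unscheduled visit by arm, so that unequal ascertainment can be seen.
- State the visit scope of the toric/non-toric summaries, and name treatment as a variable in the IOL-observation listing.

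The cost is SAP wording, one extra row in each of three tables, and one count of unscheduled visits. The downside is that the new row depends on discretionary visits and an unmasked investigator, so a difference between arms may reflect who was examined and not the lens. It would also miss findings at the extra routine visits that Protocol 10.3 does not class as unscheduled. For both reasons it should stay supplementary.
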